- Creatine Phosphokinase (CPK).
- Adrenal gland hormones: cortisol (with reflexive ACTH levels if cortisol <LLN) and dehydroepiandrosterone sulfate (DHEAS).

- Pituitary hormones: luteinizing hormone (LH) and follicle-stimulating hormone (FSH).
- Gonadal hormones: testosterone (male) and estradiol (females).
- Fat soluble vitamins: A (retinol), D (25 hydroxy vitamin D), E (alpha-tocopherol), and K (phylloquinone).
- Serum pregnancy test. Pregnancy test should be done on females of childbearing potential who are sexually active or females who have experienced menarche. The Screening (Week -2) pregnancy test should be a blood test. All other pregnancy tests will be with a local urine pregnancy test.

Notes: Any clinically relevant abnormal laboratory value should be immediately rechecked (whenever possible using the central laboratory) for confirmation before making any decision for the concerned patient. It should be documented as an AE/SAE as applicable. Please also refer to Section 10.4.

Instructions for the central laboratory will be given in a specific manual provided to each investigator.

Decision trees for the management of certain laboratory abnormalities by Sanofi are provided in [Appendix D](#).

CPK-MB and Troponin I should be performed by local laboratory and data collected in case of serious cardiac event.

Pharmacokinetic samples:

Serum samples for assessment of alirocumab concentration will be obtained periodically throughout the study as per schedule note in study flowchart of [Section 1.3](#).

For all cohorts, blood samples will be collected before IMP injection for visits 2 (Week 0), 4 (Week 4), 6 (Week 8), then for Cohorts 1 to 3 at visit 8 (Week 14/16 [for patients entering the extension phase]) and, for Cohort 4, at visit 4 (Week 4), visit 6 (Week 8), visit 7 (Week 10), and visit 8 (Week 12).

Blood samples should be collected before IMP injection.

Physical examination:

A general physical examination should be performed at the time points indicated in the study schedule flowchart [Section 1.3](#) and [Section 1.4](#). If a new clinically significant abnormality or worsening from baseline is detected after inclusion, then an AE should be reported and the patient should be considered for further clinical investigations and/or specialist consultation as per the Investigator's medical judgment.

Blood pressure (BP)/heart rate:

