11.4.4 Analyses of other endpoints

Serum total alirocumab concentrations, total and free PCSK9 concentrations will be summarized by alirocumab dose and visit using descriptive statistics. Serum concentration time profiles will be provided by alirocumab dose. Additional plots will be prepared, as deemed necessary.

Serum total alirocumab concentrations will be used for population PK modeling and the results of population PK modeling will be reported separately from the study report.

Further details will be provided in SAP.

The ADA status (positive/negative) and ADA titers will be summarized by visit using descriptive statistics. If appropriate, correlations between ADA titers, safety, and/or efficacy endpoints will be provided by graphical methods. Further details will be provided in SAP.

11.4.5 Analyses of Patient Reported Outcomes (Health-related Quality of Life/health economics variables

Not applicable.

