1.6 STATISTICAL MODIFICATIONS MADE IN THE STATISTICAL ANALYSIS PLAN

This section summarizes major changes in statistical analysis features made in approved SAP versions, with emphasis on changes after study start (after the first patient was enrolled). The statistical section of the protocol is considered as the first approved SAP.

The statistical analysis plan history table below gives the timing, rationale, and key details for major changes to the statistical analysis features in the statistical analysis plan.

Table 2 - Statistical analysis plan statistical changes

SAP version number	Date approved	Rationale	Description of statistical changes
1	15-Dec-2016	Harmonization of as-treated group definition with previous studies of the project	The alirocumab dose to be used for the as-treated analyses was changed from the dose the patient was treated with the longest duration to the dose the patient was treated with the highest number of injections (see Section 2.3.2).

SAP version number	Date approved	Rationale	Description of statistical changes
2	This version	To assess the efficacy and safety of 150 mgQ4W for body weight <50 kg / 300 mg Q4W for body weight \geq 50 kg	Addition of efficacy and safety analyses for Cohort 4 data including efficacy analyses specific to Cohort 4.
	This version	To better assess the effect of the doses.	Addition of details on the handling of patients who switch to the selected doses for Phase 3.

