2.1.5 Pharmacokinetic variables

Concentrations of total alirocumab, total and free PCSK9 in serum are assessed before IMP (pre-dose) at baseline (Week 0), Week 4, Week 8, Week 10 (for Cohort 4), Week 12 (for Cohort 4) and end of the follow-up period of OLDFI period (Week 16 for Cohorts 1& 2 or Week 14 for Cohort 3).

Pharmacokinetic variable is the total alirocumab concentration at each time point. Depending on the timing of the sample versus the previous injection, Ctrough, Cmax and CFollow-Up will be defined as follows (see also [Table 3](#)):

- Cmax for Q2W and Q4W regimens: alirocumab concentration sample taken 5 days \pm 2 days after previous injection of alirocumab;
- Ctrough for Q2W regimen: alirocumab concentration sample taken between 8 and 21 days after previous injection of alirocumab (may be just prior the next injection);
- Ctrough for Q4W regimen: alirocumab concentration sample taken between 22 and 35 days after previous injection of alirocumab (may be just prior the next injection);
- CFollow-up for Q2W regimen: alirocumab concentration sample taken more than 21 days after last injection of alirocumab and no more than 14 weeks after last injection of alirocumab.
- CFollow-up for Q4W regimen: alirocumab concentration sample taken more than 35 days after last injection of alirocumab and no more than 14 weeks after last injection of alirocumab.

Alirocumab concentration and total and free PCSK9 concentration will be described by time-point following time windows as defined in [Table 3](#) and [Table 5](#).

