2.4.7 Analyses of pharmacokinetic and pharmacodynamic variables

Concentrations of total alirocumab in serum (C_{trough} and C_{Follow-up}), free and total PCSK9 concentrations will be summarized on the PK population by visit using descriptive statistics. C_{trough,av} will be summarized on the PK population using descriptive statistics.

Time profiles for C_{trough} concentration, total and free PCSK9 will be also provided by alirocumab dose group using graphs (mean \pm SE or Median, as appropriate).

Concentrations of total alirocumab in serum and PCSK9 levels might be used for population PK modeling if considered necessary and the results of population PK modeling will be reported separately from the study report.

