2.5.4 Windows for time points

Data analyzed by time point (including efficacy, laboratory safety data, vital signs, physical examinations, ADA, PK) will be summarized using the analysis windows given in [Table 3](#) and in [Table 4](#). These analysis windows will be applicable for all analyses, and they are defined to provide more homogeneous data for time point-specific analyses.

Table 3 - Analysis windows definition for OLDFI period

Time point	Targeted study day	Analysis window in study days
Week 4	29	15 to 42
Week 8	57	43 to 63 (for Cohort 4) or 70 (for other cohorts)
Week 10 (for Cohort 4)	71	64 to 77
Week 12 (for Cohort 4)	85	78 to 92
Follow-up (for Cohorts 1 to 3) ^a	Last OLDFI IMP+10 weeks	Last OLDFI IMP+10 weeks ±4 weeks

Study days are calculated from the day of first OLDFI IMP injection, the day of first OLDFI IMP injection being Day 1. For included but not treated patients, Day 1 is the day of inclusion

^a For patients from Cohorts 1 to 3. For patients not entering the open-label extension (OLE) period or who prematurely discontinue the OLE period, only for ADA and PK.

Table 4 - Analysis windows definition for the entire study (OLDFI/OLE combined period)

Time point	Targeted study day	Analysis window in study days
Week 4	29	15 to 42
Week 8	57	43 to 63 (for Cohort 4) or 70 (for other cohorts)
Week 10 (for Cohort 4)	71	64 to 77
Week 12 (for Cohort 4)	85	78 to 92
Week 14 ^a / Week 16 ^b	Number of weeks of the planned visit x 7 +1	Targeted study day-28 to Targeted study day +27
Week 24 ^c / Week 26 ^a / Week 28 ^b	Number of weeks of the planned visit x 7 +1	Targeted study day-28 to Targeted study day +27
Week 36 ^c / Week 38 ^a / Week 40 ^b	Number of weeks of the planned visit x 7 +1	Targeted study day-28 to Targeted study day +27
Week 48 ^c / Week 50 ^a / Week 52 ^b	Number of weeks of the planned visit x 7 +1	Targeted study day-28 to Targeted study day +27
Week 62 ^a / Week 64 ^b	Number of weeks of the planned visit x 7 +1	Targeted study day-28 to Targeted study day +27
Week 74 ^a / Week 76 ^b	Number of weeks of the planned visit x 7 +1	Targeted study day-28 to Targeted study day +27
Week 86 ^a / Week 88 ^b	Number of weeks of the planned visit x 7 +1	Targeted study day-28 to Targeted study day +27
Week 98 ^a / Week 100 ^b	Number of weeks of the planned visit x 7 +1	Targeted study day-28 to Targeted study day +27
Week 110 ^a / Week 112 ^b	Number of weeks of the planned visit x 7 +1	Targeted study day-28 to Targeted study day +27

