Week 120 ^a / Week 124 ^b	Number of weeks of the planned visit x 7 +1	Targeted study day-28 to Targeted study day +27
Week 130	911	883 to 938
Follow-up ^d	Last OLE IMP+10 weeks	Last OLE IMP+10 weeks \pm 4 weeks

Study days are calculated from the day of first OLDFI IMP injection, the day of first OLDFI IMP injection being Day 1. For included but not treated patients, Day 1 is the day of inclusion.

a for Cohort 3; the 3 time points will be combined in the analysis.

b for Cohorts 1 & 2; the 3 time points will be combined in the analysis

c for Cohort 4; the 3 time points will be combined in the analysis

d For Cohorts 1 to 3 patients not entering the open-label extension (OLE) period, or who prematurely discontinue the OLE period, only for ADA.

If multiple valid values of a variable exist within an analysis window, the nearest from the targeted study day will be selected. If the difference is a tie, the value after the targeted study day will be used. If multiple valid values of a variable exist within a same day, then the first value of the day will be selected when time is available, else the scheduled visit will be selected.

PK Concentration will be analyzed as Ctrough, Cmax or Cfollow-up following time windows as defined in [Table 5](#). If the date of the previous injection is unknown, the alirocumab concentration will not be considered for the analysis.

Table 5 - Time windows for PK variables definition

PK variables	Time window (D1 = day of previous injection or day of last injection for $C_{\text{follow-up}}$)	
	Q2W regimen	Q4W regimen
Cmax	Day 4 to Day 8	Day 4 to Day 8
Ctrough	Day 9 to Day 22	Day 23 to Day 36
Cfollow-up	Day 23 to last injection + 14 weeks	Day 37 to last injection + 14 weeks

If multiple valid values satisfy the C_{max} , C_{trough} or $C_{\text{follow-up}}$ criteria, the nearest from the targeted study day (ie, Day 15/32 for C_{trough} and Day 70 for $C_{\text{follow-up}}$, Day 1 being the day of previous injection) will be selected. If the difference is a tie, the value after the targeted study day will be used.

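### The SAP gives two incompatible rules for the Cohort 4 Week 10 alirocumab concentration, and the rule that specifies the output leaves it out

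*SAP*

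**What the plan says.** Several provisions keep the Week 10 sample.

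- SAP 2.1.5 lists Week 10 among the Cohort 4 PK assessments and makes total alirocumab concentration at each time point the PK variable. It adds: "Alirocumab concentration and total and free PCSK9 concentration will be described by time-point following time windows as defined in" Tables 3 and 5.
- SAP 2.5.4 puts PK among the data analysed by time point ("physical examinations, ADA, PK) will be summarized using the analysis windows given in" Tables 3 and 4). Table 3 has a Cohort 4 Week 10 row covering study days 64 to 77.
- Protocol 11.4.4: "Serum total alirocumab concentrations, total and free PCSK9 concentrations will be summarized by alirocumab dose and visit using descriptive statistics".

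Other provisions leave it without a place.

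- SAP 2.5.4, below Table 4: "PK Concentration will be analyzed as Ctrough, Cmax or Cfollow-up following time windows as defined in" Table 5. The Q4W column has Cmax at Day 4 to 8, trough at Day 23 to 36 and follow-up from Day 37 to 14 weeks after the last injection.
- SAP 2.1.5 gives the same limits in days after injection, for example "Ctrough for Q4W regimen: alirocumab concentration sample taken between 22 and 35 days after previous injection of alirocumab".
- SAP 2.4.7 summarises total alirocumab by visit, but names only Ctrough and CFollow-up, plus Ctrough,av. Its graphs are time profiles of Ctrough "concentration, total and free PCSK9 will be also provided by alirocumab dose group using graphs".

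On precedence, SAP 1.6 says "The statistical section of the protocol is considered as the first approved SAP". SAP Table 2 lists no change that withdraws the by-visit PK summary.

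**The concern.** Two programmers could each follow the SAP and deliver different tables. One would report a Week 10 alirocumab concentration for Cohort 4 and the other would not.

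The sample at risk has a stated purpose. Protocol section 4 explains that the Week 10 visit was added to document PK and LDL-C within the Q4W dosing interval, because that regimen shows peak-to-trough variation. PK is also a secondary objective. If 2.4.7 and Table 5 are followed as written, Week 10 LDL-C and Week 10 total and free PCSK9 are reported without the drug concentration that goes with them.

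The gap had no practical effect before Cohort 4. The Q2W column of Table 5 runs without a break from Cmax to trough to follow-up, and Cohort 3 had no mid-interval sample. SAP version 2 added the Week 10 row to Table 3, but neither Table 5 nor 2.4.7 has a place for a mid-interval Q4W concentration.

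**Working it through.** **Do the two sets of class limits agree?** Table 5 counts the injection day as Day 1, so Table 5 day = days after injection + 1. From SAP 2.1.5, Q4W Cmax is 5 ± 2 = 3 to 7 days, which gives Day 4 to 8. Q4W trough is 22 to 35 days, which gives Day 23 to 36. Both match Table 5. Between Cmax and trough, 8 to 21 days (Day 9 to 22) is unassigned for Q4W. For Q2W, trough is 8 to 21 days and follow-up starts after 21, so there is no such gap.

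**Where do the scheduled samples fall?** Days since the previous injection at nominal timing, from the protocol flow charts and section 10:

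| Cohort | Visit | Days since injection | Class |
|---|---|---|---|
| 1 and 2 (each) | Week 4 | 28 − 14 = 14 | Trough |
| 1 and 2 (each) | Week 8 | 56 − 42 = 14 | Trough |
| 1 and 2 (each) | Week 16 | 112 − 42 = 70 | Follow-up |
| 3 | Week 4 | 28 − 0 = 28 | Trough |
| 3 | Week 8 | 56 − 28 = 28 | Trough |
| 3 | Week 14 | 98 − 28 = 70 | Follow-up |
| 4 | Week 4 | 28 − 0 = 28 | Trough |
| 4 | Week 8 | 56 − 28 = 28 | Trough |
| 4 | Week 10 | 70 − 56 = 14 | None |
| 4 | Week 12 | 84 − 56 = 28 | Trough |

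That is 3 + 3 + 3 + 4 = 13 samples per set of four schedules: 9 trough, 3 follow-up, 0 Cmax and 1 with no class.

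**Do the visit windows rescue it?** The interval is 14 + (Week 10 deviation) − (Week 8 deviation). All pairs of permitted days were counted:

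| Days allowed | Interval (days) | No class | Cmax | Trough | Total |
|---|---|---|---|---|---|
| Week 8 ± 3, Week 10 ± 3 | 8 to 20 | 49 | 0 | 0 | 49 |
| Week 8 ± 3, Week 10 ± 7 (protocol windows) | 4 to 24 | 89 | 10 | 6 | 105 |
| Injection on study days 54 to 60, sample on days 64 to 77 (Table 3) | 4 to 23 | 85 | 10 | 3 | 98 |

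The Cmax combinations do not help, because 2.4.7 does not report Cmax. Only a late sample reaches a reported class, and it is then labelled trough. These are counts of permitted days and say nothing about how often each would occur.

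**Tie-break days (secondary).** When several samples fall in one class, SAP 2.5.4 selects the one nearest Day 15 (Q2W trough), Day 32 (Q4W trough) or Day 70 (follow-up), with Day 1 the injection day. Day 15 is correct for 14 days. By the same convention 28 days is Day 29 and 10 weeks is 70 + 1 = Day 71, so the other two targets do not fit.

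**The case against.** The best defence is that Table 5 only attaches labels. SAP 2.1.5 names Week 10 for Cohort 4, defines the PK variable as the concentration at each time point, and introduces trough, Cmax and follow-up afterwards as depending on sample timing. SAP 2.5.4 says the Table 3 windows apply to all analyses. On that reading Table 3 governs the by-visit description, and the sample is lost only if the Table 5 sentence and the parenthesis in 2.4.7 are treated as exclusive. The SAP states no such precedence. Protocol 11.4.4 also leaves PK details to the SAP, and SAP 1.6 claims to list only major changes, so silence in Table 2 proves little.

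The permissive reading is available, and the point about Table 2 is fair. The conflict remains, however. Section 2.4.7 is where the output is specified, and it gives Week 10 alirocumab no place. The time-point sentence in 2.1.5 itself cites both Table 3 and Table 5.

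Three narrower points stand. Labelling a sample taken at least 22 days after injection as trough is what the definition intends, and a 24-day sample (injection on study day 54, sample on day 78) belongs to Week 12 under Table 3. The tie-break days matter only if unscheduled samples create duplicates. The day-count grids add little to the nominal 14-day result.

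**Conclusion.** The concern holds. Followed as written, SAP 2.4.7 and Table 5 drop the one scheduled mid-interval Q4W alirocumab concentration from every planned alirocumab summary and plot, while SAP 2.1.5, Table 3 and protocol 11.4.4 call for it to be described.

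The extent is small: one visit in one cohort of about 10 patients, 1 of 13 scheduled post-baseline samples. This assumes the Week 8 injection is given. If it were missed, the Week 10 sample would be 70 − 28 = 42 days after the last injection and would count as follow-up.

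The consequence is limited. PK output is descriptive, the primary LDL-C analysis is untouched, Week 10 LDL-C and PCSK9 are still reported, and the concentrations are still collected. Population PK modelling is only a partial safeguard: protocol 11.4.4 commits to it, SAP 2.4.7 makes it optional, and both report it separately. The point is worth correcting because the sample serves a stated secondary objective and the correction costs almost nothing.

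**What to change.** In SAP 2.4.7, state that total alirocumab concentration is summarised and plotted by dose group and Table 3 visit, including Weeks 10 and 12 for Cohort 4, whatever the Table 5 class. This restores what protocol 11.4.4 planned. The trough and follow-up summaries can stay alongside it.

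Alternatively, add a Q4W mid-interval class of 8 to 21 days after injection (Day 9 to Day 22) to 2.1.5, Table 5 and 2.4.7.

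In the same edit, change the tie-break targets to Day 29 for Q4W trough and Day 71 for follow-up, so that they fit the Day 1 convention.

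The cost is SAP wording and one extra table column. No new samples are needed.

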2.5.5 Unscheduled visits

For all parameters, unscheduled visit measurements may be used to provide a measurement for a time point, a baseline, a last or a worst value, if appropriate according to their definitions. The measurements may also be used to determine abnormal/PCSA.

2.5.6 Pooling of centers for statistical analyses

No pooling of centers will be performed for safety nor for efficacy analyses.

2.5.7 Statistical technical issues

Not Applicable

3 INTERIM ANALYSIS

There will be no formal interim analysis. However, efficacy and safety analyses will be conducted at the end of OLDFI period (main phase) for Cohorts 1 to 3 and at the end of OLDFI period for Cohort 4 to select the doses that will be used for the Phase 3 study.

Three analyses will be conducted:

- First step analysis of the OLDFI period and first step analysis of the OLDFI/OLE combined period
 - This analysis will be conducted when all patients from Cohorts 1 to 3 have completed the OLDFI period and have all the data up to follow-up period collected and validated.
 - The efficacy analyses of the OLDFI period will support the selection of the dose for the Phase 3 study. Efficacy analyses combining lipid data for OLDFI and OLE periods will be performed for exploratory purposes.
 - The safety analyses for the OLDFI/OLE combined period will not be final at the time of this analysis as it will include all data of the OLE period collected up to the common cut-off date (ie, last follow-up visit of the OLDFI period).
- Final analysis of the OLDFI period and second step analysis of the OLDFI/OLE combined period
 - This analysis will be conducted when all patients from cohorts 4 have completed the OLDFI period and have all the data from OLDFI period collected and validated.
 - The efficacy analyses of the OLDFI period will be the primary analysis of both primary and secondary efficacy endpoints and will include all data from Cohorts 1 to 4. Efficacy analyses combining lipid data for OLDFI and OLE periods will be performed for exploratory purposes.
 - The safety analyses for the OLDFI/OLE combined period will not be final at the time of this analysis as it will include all data of the OLE period collected up to the common cut-off date (ie, last visit of the OLDFI period for Cohort 4).
- Final analysis of the study
 - This analysis will be conducted at the end of OLE period with the data of OLDFI and OLE periods combined and will consist in the final analysis of the combined OLDFI and OLE periods.

Analyses methods and conventions described in the other sections of this SAP will be applied for all analyses as applicable. The following additional rules will apply for analyses of combined OLDFI and OLE periods performed at first analysis:

- Patients without end of treatment visit performed at the time of the cut-off date will be considered as ongoing and exposed up to the cut-off date. Therefore:

- Patients who did not complete treatment period nor prematurely discontinued the study treatment at cut-off date will be analyzed as “ongoing” in the disposition summary.
- Their OLDFI/OLE combined TEAE period, treatment period and on-study observation period will end at the cut-off date.
- Their treatment duration will be derived by considering date of cut-off as last injection date.
- Analyses of number of injections, mean injection frequency, percentage of days with under/above-planned dosing and compliance will be performed up to the last injection reported in the e-CRF up to the cut-off date.
- AEs occurring, worsening or becoming serious after the cut-off date will not be included in the analyses. However, any available outcome before database lock, regardless of timing in relation to the cut-off date, of an adverse event starting prior to the cut-off date will be taken into account. Medications, treatment discontinuations/completions and deaths occurring after the cut-off date will not be included in the analyses.
- Post-treatment period, post-study period are not applicable for ongoing patients. Analyses of post-treatment AEs, post-study deaths and post-treatment medications will be performed for patients who either completed or prematurely discontinued the treatment before or at the cut-off date.
- Analysis of status at last study contact and proportion of patients with insufficient follow-up will be provided for patients who completed the follow-up before or at the cut-off date. Follow-up will be considered completed if one of the following conditions is met: cut-off - last injection date \geq 77 days OR last contact filled in regardless of contact method OR follow-up visit performed.

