2.4.3.1 Extent of investigational medicinal product exposure

The total exposure to IMP will be assessed using the following parameters:

- Duration of OLDFI IMP injection exposure in weeks defined as (date of last OLDFI IMP injection – date of first OLDFI IMP injection + 14 days)/7 (for Cohorts 1& 2) or (date of last OLDFI IMP injection – date of first OLDFI IMP injection + 28 days)/7 (for Cohorts 3 & 4), regardless of unplanned intermittent discontinuations.
- The total number of OLDFI IMP injections by patient.
- For Cohorts 1 to 3, and for the OLDFI/OLE combined period the following parameters will be derived up to, and post switch of dose:
 - Duration of OLDFI/OLE combined period IMP injection exposure up to the switch to Phase 3 doses in weeks, defined as (date of last IMP injection up to the switch – date of first IMP injection + 14 days)/7 (for Cohorts 1& 2) or (date of last IMP injection up to the switch – date of first IMP injection + 28 days)/7 (for Cohorts 3 & 4), regardless of unplanned intermittent discontinuations.
 - Duration of IMP injection exposure post switch in weeks, defined as: (date of last IMP injection +14 – date of first IMP injection post switch)/7, regardless of intermittent discontinuations.
 - Total number of OLDFI/OLE combined period IMP injections up to, and post switch of dose.
- For Cohort 4, and for the OLDFI/OLE combined period, the following parameters will be derived:
 - Duration of OLDFI/OLE combined period IMP injection exposure in weeks, defined as (date of last IMP injection – date of first IMP injection + 28 days)/7, regardless of unplanned intermittent discontinuations.
 - Total number of OLDFI/OLE combined period IMP injections.
- For duration of IMP injection exposure calculation, see [Section 2.5.3](#) for calculation in case of missing or incomplete data. Non-integer values will be rounded to one decimal place.

Duration of OLDFI IMP exposure will be summarized descriptively as a quantitative variable (number, mean, SD, median, minimum, and maximum) and categorically using the following categories: ≥ 1 day to <1 week, ≥ 1 to <3 weeks, ≥ 3 to <5 weeks, ≥ 5 to <7 weeks, ≥ 7 to <9 weeks, ≥ 9 to <11 weeks, ≥ 11 weeks.

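### For patients still on treatment at the step-analysis cut-off, the SAP rule read with its own exposure formula runs exposure two or four weeks past the cut-off

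*SAP*

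**What the plan says.** SAP section 3 gives extra rules for combined-period (OLDFI/OLE) analyses done at the first analysis. A patient with no end-of-treatment visit by the cut-off is "considered as ongoing and exposed up to the cut-off date". What follows is presented as a consequence of that:

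- All three of these patients' time windows (TEAE, treatment and on-study) close when the data are cut.
- "Their treatment duration will be derived by considering date of cut-off as last injection date".
- Injection counts, injection frequency and compliance use the injections actually recorded up to the cut-off.

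Section 3 also carries over the methods and conventions of the other SAP sections where they apply.

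SAP section 2.4.3.1 holds the only duration formulas. For the combined period before any switch to Phase 3 doses, Cohorts 1 and 2 use "date of last IMP injection up to the switch – date of first IMP injection + 14 days)/7" and the Q4W cohorts use "date of last IMP injection up to the switch – date of first IMP injection + 28 days)/7". After the switch the formula is "date of last IMP injection +14 – date of first IMP injection post switch)/7". Cohort 4, which does not switch, also adds 28 days. The results feed a summary of duration, a table of duration categories and cumulative exposure in patient-years.

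**The concern.** The 14 or 28 days stand for the dosing interval that a real last injection covers. The cut-off is an administrative date, not an injection. Entering it as the last injection and keeping the added interval credits every ongoing patient with a full interval after the date on which section 3 says exposure stops, whenever the last real injection was given.

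The overstatement is about twice as large for Q4W as for Q2W, so it does not cancel when regimens are set side by side. It also moves patients near a category boundary into the next exposure category and inflates cumulative patient-years.

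**Working it through.** **Inputs.** Duration formulas: SAP 2.4.3.1. Ongoing-patient rule: SAP section 3. Planned injection times (last at Week 6 for Cohorts 1 and 2, Week 4 for Cohort 3, Week 8 for Cohort 4): Protocol 6.1. Number treated in Cohorts 1 to 3 (31): Protocol section 4. The cohort split of those 31 and the number ongoing at the cut-off are not given.

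**Step 1: the formula on planned dates.** Duration in weeks = (last − first + 14 or 28)/7.

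- Cohorts 1 and 2: (42 + 14)/7 = 8 weeks
- Cohort 3: (28 + 28)/7 = 8 weeks
- Cohort 4: (56 + 28)/7 = 12 weeks

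These match the planned treatment periods, so the added days are indeed the interval after a real last injection.

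**Step 2: the rule for ongoing patients.** Setting last = cut-off gives (cut-off − first + 14 or 28)/7. Exposure stopped at the cut-off is (cut-off − first)/7, or (cut-off − first + 1)/7 if the cut-off day is counted. The excess is 14 or 28 days on the first count and 14 − 1 = 13 or 28 − 1 = 27 days on the second.

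**Step 3: examples, cut-off day counted.**

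| Patient | Days from first injection to cut-off | Literal rule | Stopped at cut-off | Excess |
|---|---|---|---|---|
| Cohort 3, Week 14 | 98 | 126/7 = 18.0 wk | 99/7 = 14.1 wk | 27/99 = 27% |
| Cohort 1 or 2, Week 16 | 112 | 126/7 = 18.0 wk | 113/7 = 16.1 wk | 13/113 = 12% |
| Q2W, Week 52 | 364 | 378/7 = 54.0 wk | 365/7 = 52.1 wk | 13/365 = 3.6% |
| Q4W, Week 52 | 364 | 392/7 = 56.0 wk | 365/7 = 52.1 wk | 27/365 = 7.4% |

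**Step 4: total, as an assumed upper bound.** Take all 31 patients as ongoing and unswitched.

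- 20 Q2W and 11 Q4W: 20 × 13 + 11 × 27 = 260 + 297 = 557 days; 557/365.25 = 1.5 patient-years.
- 21 Q2W and 10 Q4W: 21 × 13 + 10 × 27 = 273 + 270 = 543 days; 543/365.25 = 1.5 patient-years.
- If instead all 31 had switched, only the post-switch formula meets the cut-off: 31 × 13 = 403 days; 403/365.25 = 1.1 patient-years.

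The extension is optional, so the true figure is smaller if fewer patients were ongoing, down to zero if none were.

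**The case against.** **The intent is clear.** Section 3 does not itself say to add 14 or 28 days; that comes from joining it to 2.4.3.1. It states that exposure stops at the cut-off and carries other conventions over only where they apply, so a programmer could fairly drop the interval. Part of this stands: the intent is plain and the defect lies in the derivation. But no text drops the days and no other duration formula exists. The label in section 3 is treatment duration rather than injection exposure, but SAP 2.5.3 uses treatment duration and exposure duration for the same quantity.

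**A different comparator halves the error.** The ordinary formula with a real last injection also credits time past the cut-off. Against that convention, with on-schedule dosing, the excess is 0 to 14 days for Q2W or 0 to 28 days for Q4W, about half the size on average. This is correct arithmetic, but section 3 names the cut-off as the end of exposure, so the cut-off is the comparator here.

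**The stronger reading.** A reader might infer that safety rates are diluted because exposure time no longer matches adverse event observation time. The documents do not support that. Patient-year event rates (SAP 2.4.5.1) use the TEAE period, which stops at the cut-off for ongoing patients. Exposure, treatment and TEAE periods also end at different times by design (14 or 28, 21 or 35, and 70 days after the last injection), so a mismatch between them is not in itself an error.

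**Exposure is not pure on-drug time anyway.** For Cohorts 1 to 3 the combined span runs from the first dose-finding injection and includes the planned 6 to 8 off-treatment weeks. That is true, and the fix below leaves it in place; it is a separate property of the definition.

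**Timing.** Protocol section 4 already reports Week 8 results for Cohorts 1 to 3, so the first-step work may predate this SAP version. The documents do not settle this. If it does, the value of the correction lies in the second-step analysis.

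**Conclusion.** The point holds as a minor error in a stated derivation. Taken literally, the SAP ends exposure 14 days (Q2W or post-switch) or 28 days (unswitched Q4W) after the date on which it says exposure ends; 13 or 27 days if the cut-off day counts. The per-patient size follows from the formulas alone. The total of about 1.5 patient-years is an upper bound that assumes all 31 patients ongoing and unswitched, with an assumed regimen split.

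The reach is narrow: interim combined-period duration, its categories and cumulative patient-years. Dose-finding-period exposure is untouched, and the final analysis has no ongoing patients. Section 3 writes the rule for the first analysis only. It plans a second-step combined analysis with its own cut-off, when extension patients may still be on treatment, and gives no explicit ongoing-patient rule for it.

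**What to change.** In SAP section 3, replace the sentence on treatment duration with a definition: for patients ongoing at the cut-off, duration in weeks = (cut-off date − first injection date + 1)/7, with no added dosing interval. For post-switch exposure, count from the first post-switch injection. State that the same rule applies to patients still ongoing at the second-step analysis, including Cohort 4.

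The cost is one or two sentences in the SAP and one line in the derivation program. No data collection, estimand or efficacy analysis changes. If first-step exposure tables have already been produced, check which version of the derivation they used.
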